 - (1) “The purpose of this test is to find your judgments of the loudness of different sounds. You will hear sounds that increase and decrease in volume. You must make a judgment about how loud the sounds are. Pretend you are listening to the radio at that volume. How loud would it be? After each sound, tell me which of these categories best describes the loudness. Keep in mind that an uncomfortably loud sound is louder than you would ever choose on your radio no matter what mood you are in.”
- c. Stimuli: warble tone at 500 Hz followed by 3000 Hz
- d. Participant will respond to varied presentation levels on seven-point scale of loudness using the Categories of Loudness (1-8) as a reference.
- e. Procedure: start at threshold and use an ascending approach in 5 dB steps until an “uncomfortably loud” response is obtained. Return to threshold and repeat for a total of 4 times.
- f. The median of the values obtained on four runs may be assumed to represent the loudness percept in each category.

- g. Record on audiogram.
7. Put bone vibrator on participant's mastoid and administer pure-tone bone-conduction (BC) testing using ASHA standard procedures using the GSI 61 audiometer. Set "transducer" to "bone".
- a. BC test frequencies: 250, 500, 1000, 1500, 2000, 3000, and 4000 Hz. Apply masking as needed.
8. To be eligible for ABCD, participant's hearing thresholds need to be bilaterally symmetrical and within a mild to moderate sensorineural hearing loss range, and within fitting range of hearing aid. *See shaded region on Audiogram (1-6).
- a. Asymmetry: more than 20 dB difference at any one frequency 250-2000 Hz makes participant ineligible.
 - b. Participant may have one threshold at a single frequency in each ear that is outside the shaded area by ≤ 10 dB and still be eligible for study.
 - c. If participant's thresholds are close to, but outside our accepted range, "flag" the file and notify PI and CTC.
 - d. If participant is eligible, continue with unaided CST.
 - e. If ineligible, counsel (see H below).
- (1) Note on audiogram if a referral to ENT was made or other advice was given.

G. UNAIDED CST (CONNECTED SPEECH TEST) FORM (1-9)

- 1. Audiometer settings:
 - a. Track 1: Calibrate—complete prior to every test
 - b. Channel 1: 50 dB HL, External A, Left (front speaker), Speaker
 - c. Channel 2: 46 dB HL, External B, Right (back speaker), Speaker

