 - (b) Select the “Client ID” box and enter file name and press “Continue”. This will save file in “Sessions” folder on USB flash drive along with a style sheet (audioscan.xml).
- h. When RECD measurements are complete for both ears, disinfect probe tubes with two disinfectant wipes, dry with paper towel, and place in envelope with participant number on it which will go in folder.
- i. Print RECD measurements from USB flash drive and place in Session 1 folder.

- j. Take participant and participant's folder to CTC.

M. SESSION 1 CHECKLIST (1-14)

1. Ensure all portions of the checklist are completed.

N. STUDY CONSENT FORM #2 (1-15A FOR TYPICAL PURCHASE PRICE GROUP OR 1-15B FOR REDUCED PURCHASE PRICE GROUP), MEDICAL WAIVER (1-16) AND ELIGIBILITY PART 2 (1-17)

1. CTC reviews the general nature of the study including approximate number of sessions and the requirement to purchase hearing aids.
2. CTC informs participant of the FDA requirement for medical clearance. If participant elects to waive the right to medical evaluation/clearance and is interested in participating in the clinical trial, he or she will sign the Study Consent Form #2 (1-15a or 1-15b) and the Medical Waiver (1-16).
 - a. If participant does not waive the medical evaluation and clearance, the participant is not eligible for the study. Only participants who choose to waive medical clearance prior to hearing aid purchase are accepted to the study. If participant does not wish to waive medical evaluation and clearance, participant should be referred to the IU Hearing Clinic.
3. CTC will complete Eligibility Part 2 (1-17). If the answer to any of the exclusion criteria questions is "yes", the participant is not eligible.
4. If participant is not eligible, or is eligible but does not want to participate in study, CTC will cancel the Session 2 appointment and escort participant out of building.
5. If participant agrees to participate, signs Study Consent Form #2 (1-15a or 1-15b), completes the Medical Waiver (1-16), and does not answer "yes" to any of the exclusion criteria, CTC will assign participant to one of 6 possible treatment groups.

- a. Using the unaided CST score, CTC will place participant in a low ($\leq 40\%$ correct), medium ($40\% < \text{score} < 68\%$), or high ($\geq 68\%$ correct) performance group, and use this information for randomizing the participant into a treatment group.

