- b. Participant groups are stratified by purchase price. For the initial half of the study, participants are randomized into treatment groups (AB, CD, P) using the typical purchase price (TPP). Then, for roughly the second half of the study, participants are randomized into treatment groups using the reduced purchase price (RPP).

Within each purchase price group, subjects are randomized to one of three treatment groups: audiology-based (AB), placebo (P-AB), or consumer-decides (CD) using pre-generated random orders yielding roughly equal proportions of AB, CD and P group assignments. The possible treatment groups include: P-AB/TPP, P-AB/RPP, AB/TPP, AB/RPP, CD/RPP, and CD/TPP. (NOTE: Sect 5.b, was edited AFTER STUDY COMPLETION to reflect what actually took place. The shared protocol manual used by the Clinical Trials Group indicated that the purchase price was also RANDOMLY DETERMINED for each participant enrolled. Audiologists A1, A2, A3 and A4 were unaware of this deception re: the ordering of purchase price assignment as was confirmed in individual interviews with the audiologists by the PI at study completion.)

- c. Depending on the purchase price being used, CTC discusses the purchase price with the participant, which is due, in full, at the time of Session 2.
 - d. CTC informs the participant that a 16.7% discount on purchase price will be provided by the completion of 3 sessions.
6. CTC tells participant: “The audiologists are involved in only the research portion of this

project; therefore, they will not know information about purchase price. I am the business contact, so if you have questions please contact me.” CTC gives participant a business card.

7. At this time, CTC verifies the appointment to come in the next day for Session 2.
8. A copy of the participant’s completed Audiogram (1-6), RECD measurements, and an envelope containing the probe tubes used during RECD should be placed in Session 2 folder for hearing aid programming.

II. SESSION 2 –ARL: 120-150 MINUTES REQUIRED

Study personnel

CTC: Clinical Trials Coordinator

A1: Audiologist 1

A2: Audiologist 2

A3: Audiologist 3

Components

- A. CTC- UNAIDED PHAP (T-1)
- B. CTC- UNAIDED HHIE (T-2)
- C. A1/A2/CTC- HEARING AID SELECTION AND/OR FITTING (BASED ON GROUP ASSIGNMENT)
 - 4. AUDIOLOGY-BASED (AB) GROUP: PAGES 20-28
 - 5. PLACEBO (P-AB) GROUP: PAGES 28-34
 - 6. CONSUMER-DECIDES (CD) GROUP: PAGES 34-36
- D. UNSCHEDULED VISITS (M-1)

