 - (e) Click “Equalize” while hearing aids are still muted. After noise has stopped, un-mute hearing aids.
- (5) Run speechmap with “carrot passage” speech stimulus at 65 dB SPL and then fine-tune gain until it matches targets appropriately.
 - (a) Target-matching rule: for 250 through 4000 Hz, all measured values within 4 dB of target at all frequencies in this range is the goal, but will accept fit after initial fine-tuning attempts if within 7 dB of target at all frequencies in this range.
 - (b) If unable to meet + or – 7 dB criterion, participant will not be exited from the study, but we will likely need to replace that participant in the study. If this happens, “flag” the file and let PI and CTC know.
- (6) Run speechmap at 55 dB SPL and 75 dB SPL. Do not fine tune hearing aids following these measurements.
- (7) Record SII measurements for 65, 55, and 75 dB SPL inputs for both ears on Session 2 Audiologist Checklist (2-1).
 - (a) Do not make hearing aid adjustments based on participant feedback until outcome measures are completed in Session 3.

- f. Loudness discomfort measurement
- (1) Categories of Loudness (1-8) should be in front of participant (participant was familiarized with this during audiologic evaluation).
 - (2) Re-familiarize participant with loudness categories and instruct:
 - (a) “You will hear several loud beeps that get higher in pitch. The beeps will be loud, but if they get “uncomfortably loud” (refer to Categories of Loudness), raise your hand. The beeps are very quick, so try to raise your hand as quickly as possible. We can repeat if necessary.”
 - (3) Run the 85 dB SPL MPO stimulus with the hearing aid on in right ear only. Left hearing aid should be muted.
 - (4) If participant indicates a tone is “uncomfortably loud”, decrease maximum output at corresponding frequency respectively by 4 dB, record on Session 2 Audiologist Checklist (2-1), and re-initiate 85 dB SPL stimuli.
 - (5) Continue until “uncomfortably loud” responses are no longer obtained.
 - (6) Repeat with left hearing aid on and right hearing aid muted.
 - (7) Finally, turn both hearing aids on and run the MPO stimulus. If participant reports none of the sounds are “uncomfortably loud” move on to programming VC (g). If participant reports one of the sounds uncomfortably loud, determine which frequency to lower by 2 dB in both hearing aids until “uncomfortably loud” response is no longer obtained. Record any adjustments on Session 2 Audiologist Checklist (2-1).

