- (1) Gives participant 8.35% discount, and collects full payment for hearing aids.
- (2) Refers to light blue Hearing Aid Decision Form for Audiologist (2-2) to determine which size of extra domes to place in participant's hearing aid kit.
- (3) Records participant's hearing aid information (serial numbers, warranty info,

battery size, etc.) in the User Guide (2-4) on the inside of the front cover.

- (4) Provides participant with hearing aid kit containing batteries, cleaning tools, extra domes, User Guide, etc.
- (5) Opens hearing aid kit to verify presence of all required items. Checks these items on the Hearing Aid Case Checklist for CTC (2-5). If the participant has any questions regarding contents, CTC will tell the participant to refer to the User Guide.
- (6) Schedules participant's Session 3 appointment time for six weeks (\pm one week) after Session 2, providing him or her with parking pass and reminder card with the CTC's contact number.
- (7) Emphasizes the importance of calling CTC if questions or problems arise, and escorts participant out of the building.

5. Placebo group hearing aid selection and fitting

- a. If participant is one of the 20% that are designated tulip-dome fittings, the post-it will read ("P Tulip") letting A1/A2 know that a tulip dome should be used with this participant instead of an open dome. (NOTE: given 0-dB insertion gain, a tulip dome would most likely never be needed by placebos; therefore, the presence of a tulip dome could potentially tip off the blinded audiologist regarding group assignment. This led to use of 20% tulip domes for placebos.)
- b. A1/A2 escorts participant to participant side of audio booth.
- c. Turn chair and place within marks on the floor and position the external speaker within the marks on the floor for real-ear testing. Participant is seated in this chair for hearing aid programming.
- d. Hearing aid color and dome choice

- (1) Participant chooses hearing aid color. Audiologist chooses appropriate dome size and tubing length using hearing aid manufacturer's tubing measurement tool.
- e. Program hearing aids
- (1) Audiologist places Audiogram (1-6) on lap to be in view of the participant to mimic what occurs in typical audiology clinic.
 - (2) Enter participant number and audiogram into Noah, then click Aventa in upper right corner.
 - (3) Connect hearing aid and generate first fit in the manufacturer's fitting software using NAL-NL2 fitting algorithm.

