 - (4) Fitting should default to "Experienced Non-Linear".
 - (5) Select "Fitting" tab (top toolbar) and turn "Binaural Correction" off.
 - (6) Change "Physical Properties" to the size of tube and dome chosen.
 - (7) Change P1 to "Basic+Softswitching" if it is not already on that setting.
 - (a) Directionality: Fixed (Omni as of 5/5/2014)
 - (b) Expansion: Off
 - (c) Noise Tracker II: Per Environment
 - (d) Wind Guard: Off
 - (8) Click on "Environmental Optimizer" and click "Reset to..." then select "0 dB" so that all levels are at zero.
 - (9) If applicable, click on "Tinnitus Sound Generator" and ensure it is off.
- f. Real-ear insertion gain using Verifit
- (1) Prior to completing Verifit tests, enter zeros for audiogram thresholds and enter

participant's measured RECD into Verifit.

- (2) "Tests" → "On-ear measures" → "Insertion Gain" (65-dB-SPL pure tones)
- (3) Insert one probe tube in each ear.
 - (a) Check that the probe tube is connected to the appropriate right or left cord.
 - (b) Check that each reference microphone is facing outwards.
- (4) Select "Audiogram" and change "REUR" to "measure".
- (5) Measure REUR for both ears (probe tubes are only things in ears).
- (6) After REUR is measured in both ears, insert hearing aids and measure REAR using a 65 dB SPL tonal sweep for both ears.
- (7) Fine tune gain in software to make REIG response as close to zero as possible.
- (8) If REIG is too high: Use "Environmental Optimizer" settings to reduce REIG (these settings must change equally for all environments and can only be reduced down to a maximum of 6 dB).
- (9) If REIG is too low: use gain adjustment to increase gain at specific frequencies.
- (10) Change format settings to "Table".
- (11) Insert USB flash drive into Verifit USB port.
 - (a) Select "Print" and enter file name and press "Continue" to save to USB flash drive.
- (12) Disinfect both probe tubes with two disinfectant wipes, dry with paper towel, and place in envelope with participant # labeled on front.

g. Program VC

- (1) Click "copy" with "P1" (Program 1) gain settings visible.
- (2) Click on "P2" and click "paste".

- (a) Select “all” gain values on “P2” frequency gain response and increase overall gain +1 dB.
- (3) Click on “P3” and click “paste”.
 - (a) Do not make any gain changes to this program.
- (4) Click on “P4” and click “paste”.
 - (a) Select “all” gain values on “P4” frequency gain response and increase overall gain by +3 dB.
- (5) Return to “P1”.

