 - (6) Three partitioned bins (beige bin, brown bin, and grey bin) each with two X hearing aids, two Y hearing aids, and two Z hearing aids [programmed according to section #9 of the New Hearing Aid Check-in Protocol (M-2)] in each partition

- (7) Two bins (left/right) with four partitions for slim tube choices (0B, 1B, 2B, 3B)
 - (8) One bin with four partitions for dome choices (S, M, L, tulip)
 - (9) Black bin labeled “No” for pieces that were tried, but unwanted
 - (10) Three instruction binders [black (2-7), red (2-8), blue (2-9)]
- c. CTC starts the introduction video on the Samsung tablet for the participant.
 - d. When the video is over, CTC gets the Samsung tablet from the participant, and reminds him or her that the participant should begin choosing their hearing aid by reading through the binders [starting with the black binder (2-7)].
 - e. CTC instructs participant to press button on pager system when he or she has made a hearing aid selection for both ears then leaves Clinical Trials Hearing Aid Room.
 - f. Participant chooses hearing aid (2-7), (2-8), (2-9)
 - (1) Participant selects which aid (X, Y, Z), color (beige, brown, grey), tubing (0B, 1B, 2B, 3B), and tip (S, M, L, tulip) by reading the black (2-7), red (2-8) and blue (2-9) binders, then pages CTC.
 - g. CTC re-enters CD room and closes the Push and Play by tapping “X” in the upper right corner and prints the results.
 - (1) CTC records details of the unwanted hearing aids, tubes, and/or domes in the black bin and records this on the Hearing Aid Decision Form for CTC (2-10).
 - h. CTC escorts participant (and guest) into the CTC office and does the following:
 - (1) Reviews what the participant filled out on the Rx Form (2-6), and records hearing aid models, serial numbers, slim tube size and dome size on Hearing Aid Decision Form for CTC (2-10)
 - (2) Verifies the serial numbers of the selected hearing aids match up with the

appropriate X, Y, or Z programming indicated on the CD check-in chart

- (3) Records dates and initials next to each hearing aid purchased on the CD check-in chart
- (4) Removes the sticker on hearing aid signifying “X”, “Y”, or “Z”
- (5) Marks the right hearing aid with the red indicator and the left hearing aid with the blue indicator and explains to participant what these colors indicate
- (6) Gives participant 8.35% discount, and collects full payment for hearing aids

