 - b. CTC or A4 will fill out Exit Form #2 (3-11).
6. These decisions will be recorded on Hearing Aid Status Form #1 (3-10).

M. PROGRAMMING AND/OR ADJUSTMENT OF HEARING AIDS (3-7)

1. If DFS must be run in addition to programming changes, it should be completed in the following order:
 - a. Programming changes
 - b. Run and save post-adjustment simulated speechmaps in testbox.
 - c. Run DFS.
 - d. Run and save post-DFS simulated speechmaps in testbox.
 - (1) If this order cannot be maintained, note this in screenshot and XML file names so that data will not be used.
2. AB group (not including Placebo)
 - a. Complete any fine-tuning that the participant requests based on participant feedback. A program swap is not considered fine-tuning/adjustment.
 - (1) Ensure RECD and audio are entered in Verifit.
 - b. Run real-ear speechmap for “carrot passage” for both ears at 65, 55, and 75 dB SPL and MPO at 85 dB SPL.
 - c. Record SIIs for 65, 55, and 75 dB SPL stimuli on Session 3 Checklist (3-7).
 - d. Discard sticky tack.
 - e. Change format settings to “Table”.
 - f. Select “Print” and enter file name and press “Continue” to print to USB.
 - (1) Save as an XML file.
 - (a) Press “Session” on Verifit, then select “Store session file”.
 - (b) Select the “Client ID” box and enter file name and press “Continue” (refer to file naming nomenclature sheet in booth). This will save the file in “Sessions” folder on USB stick along with a style sheet (audioscan.xsl).
3. Placebo and CD groups

- a. Reprogram hearing aids in accordance with NAL-NL2 prescription procedure.
 - (1) Ensure participant's RECD and audio are entered in to the Verifit.
- b. Use Verifit in the sound booth to run real ear speechmap at 65 dB SPL for "carrot passage" to verify target gain (NAL-NL2).
 - (1) Adjust gain in Aventa as needed until targets are matched appropriately.
 - (2) Target-Matching Rule: For 250 through 4000 Hz, all measured values within 4 dB of target at all frequencies in this range is the goal, but will accept fit after initial fine-tuning attempts if only within 7 dB of target at all frequencies in this range.
- c. Run speechmap at 55 dB SPL and 75 dB SPL.
- d. Record SIIs for 65, 55, and 75 dB SPL stimuli on Session 3 Checklist (3-7).
- e. Run 85 dB SPL pure tone sweep (MPO) stimulus to verify maximum output isn't uncomfortably loud/painful.
 - (1) Re-familiarize participant with loudness categories and instruct:

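### A replacement rule triggered after randomisation, in the AB arm only, could take hard-to-fit participants out of AB while P and CD keep theirs; the effect is probably small

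*Protocol*

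**What the plan says.** **Assignment.** Protocol section I.N.5 places allocation at the end of Session 1, once consent and eligibility are complete: "CTC will assign participant to one of 6 possible treatment groups". Section I.N.5.b describes the only allocation route, "using pre-generated random orders yielding roughly equal proportions of AB, CD and P group assignments", within each purchase-price group.

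**The AB rule.** At Session 2 (II.C.4.e(5)), AB aids are adjusted to the NAL-NL2 target. The goal is within 4 dB from 250 to 4000 Hz, and a fit within 7 dB at every frequency in that range is accepted. If 7 dB cannot be met, item (b) says the "participant will not be exited from the study, but we will likely need to replace that participant in the study". The file is flagged and the principal investigator and the trials coordinator are told.

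**The other arms at Session 2.** The placebo instruction (II.C.5.f(7)) is "Fine tune gain in software to make REIG response as close to zero as possible", with no numerical tolerance and no replacement clause. CD participants choose among pre-programmed aids (II.C.6.f), and no target match is measured.

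**Session 3.** The 7 dB rule reaches P and CD only in III.M.3 ("Reprogram hearing aids in accordance with NAL-NL2 prescription procedure"). That step follows the outcome measures and the disclosure of group, and no replacement is attached to it.

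**The concern.** The trigger is a fitting result obtained after randomisation, and before outcomes only AB can produce it. That asymmetry follows from what the arms receive, but it means the rule acts on AB alone. The rule is also discretionary. It does not say who decides or what turns a likely replacement into an actual one. Nor does it say whether the newcomer takes an AB place or the next random assignment, or whether the original still counts in AB.

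If the newcomer stands in for the original, AB loses a type of participant that P and CD retain. Should missing the target be related to outcome, both AB contrasts are biased. The direction cannot be known in advance: AB is favoured if hard-to-fit ears do worse and disfavoured if they do better.

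**Working it through.** The Protocol states no sample size, failure rate or outcome difference, so there is no planned figure to reproduce. The calculation below is a sensitivity check on assumed values.

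**Assumptions.** f = share of AB fits that miss 7 dB; d = mean outcome of passed fits minus failed fits, in SD units; n = participants per group (30, 50 or 100).

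**Case 1: originals displaced.** AB then holds only passed fits. Its mean differs from that of all randomised AB participants by

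shift = f × d.

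| f | d | shift (SD) |
|---|---|---|
| 0 | any | 0 |
| 1% | 0.3 | 0.003 |
| 5% | ±0.5 | ±0.025 |
| 10% | ±0.5 | ±0.05 |

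**Effect on the error rate.** The standard error of a two-group difference is √(2/n) SD. With z = shift / SE, the two-sided error at nominal 5% is Φ(−1.96 + z) + Φ(−1.96 − z). The middle columns take a shift of 0.05 SD.

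| n per group | SE | z at 0.05 SD | error rate | shift giving 10% error | f needed at d = 0.5 |
|---|---|---|---|---|---|
| 30 | 0.258 | 0.194 | 5.4% | 0.168 SD | 34% |
| 50 | 0.200 | 0.250 | 5.7% | 0.130 SD | 26% |
| 100 | 0.141 | 0.354 | 6.4% | 0.092 SD | 18% |

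The last column is the shift divided by 0.5.

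**A harsher assumption.** With f = 20% and d = 1.0 the shift is 0.20 SD, and the error rate at 50 per group is 17%. The problem becomes material only if both f and d are large.

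**Case 2: originals kept, people added** (n = 50, f = 10%, d = 0.5).

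- One passing addition for each of 5 failures: the flagged share falls to 5/55 = 0.0909, and the shift is (0.10 − 0.0909) × 0.5 = 0.0045 SD.
- Adding AB participants until 50 have passed: the number of failures is negative binomial and the mean flagged share is 0.0982, so the shift is (0.10 − 0.0982) × 0.5 = 0.0009 SD.

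The reading of the clause therefore decides the matter. For the same f and d, displacement gives 0.05 SD and retention 0.001 to 0.005 SD.

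**How large f might be.** Section I.F.8 requires, before randomisation and in all arms, thresholds that are "bilaterally symmetrical and within a mild to moderate sensorineural hearing loss range, and within fitting range of hearing aid". That should make failures uncommon, although the Protocol foresees enough of them to write a rule.

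**The case against.** The strongest reply is that the harmful reading adds words to the text. The clause does not say that the substitute enters AB or that the original's data are dropped, and it opens by saying the participant is not exited. The AB steps that follow have no branch for flagged fits. They run on to the "Session 3 appointment time for six weeks" (II.C.4.k(6)), and the Session 3 outcome measures exclude nobody for a poor fit. The only allocation route described is the random order, so a new enrollee would take whatever group came next. Who is analysed may be settled in a statistical analysis plan that is not shown. The assumed d may also overstate the error inflation for AB versus P: if the fitting has no effect, a poor match cannot itself worsen outcome, and only prognostic differences between ears would count.

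Most of this stands. Retention is a fair reading, the effect is probably small, and no finding is made here about a missing analysis population. But replacing a participant ordinarily means substitution, and nothing in the clause rules that out. An analysis plan could say whose data count; it would not by itself say how a replacement is enrolled and allocated. That is trial conduct, and the Protocol has written an ambiguous rule for it.

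The note in I.N.5.b says that item was edited after study completion. Enrolment therefore appears to be over, and a change of wording can no longer alter conduct. That affects the form of the fix, not the need for it.

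**Conclusion.** The concern holds, in conditional form. The Protocol contains a discretionary replacement rule that operates after randomisation and in AB alone. Applied as substitution, it would mean that AB versus P and AB versus CD do not compare the groups as randomised. Applied as retention plus addition, it does almost no harm.

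Under substitution with f up to 10% and |d| up to 0.5, the shift is at most 0.05 SD in either direction. The corresponding error rate is at most 5.4% to 6.4% for 30 to 100 per group. These figures rest entirely on assumed f, d and n and on a normal approximation. The bias is zero if no fit fails or if everyone randomised is analysed as assigned with no selective replacement. It should be fixed because removing the doubt costs almost nothing, not because a large bias is likely. Confidence is medium, since the text supports both readings.

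**What to change.** Delete the replacement clause in II.C.4.e(5)(b). Alternatively, keep it and state that any additional participant enters through the next place in the pre-generated random order covering all groups, and displaces nobody. In either case, state that every randomised participant is analysed in the assigned group whether or not the 7 dB criterion is met, and that the flag serves only a labelled sensitivity analysis. If enrolment has closed, the same sentences should record how many AB participants were flagged, whether any were replaced, how replacements were allocated, and how the originals were analysed.

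The cost is one or two sentences. Deletion needs no extra visits or participants, because flagged participants already stay in follow-up. The AB estimate may move slightly in either direction. Adding people through the random order may leave group sizes slightly unequal. At roughly one-third allocation, each extra AB participant takes about 1 / (1/3) = 3 enrolments, so 5 flagged participants would take about 15. No fitting target or clinical rule changes.
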